3 OBJECTIVES

3.1 Primary Objectives

- **Phase I:** To evaluate the safety of the combination of durvalumab with nintedanib in patients with unresectable Stage II/III/oligometastatic IV NSCLC
- **Phase II:** To compare the rate of symptomatic radiation pneumonitis at 6 months after completion of chemoradiation in patients with unresectable Stage II/III/oligometastatic IV NSCLC who completed chemoradiation followed by nintedanib versus placebo.

3.2 Secondary Objectives

- To compare the quality of life (QOL) in patients who received nintedanib versus placebo during active treatment until 6 months after completion of treatment.
- To compare the progression-free survival, overall survival and 1-year progression-free survival rate in patients who received nintedanib versus placebo.
- To compare pulmonary function test (PFT) results and RP score in patients who received nintedanib versus placebo.
- To compare the composite index (based on PFT, RP score and QOL) at the end of active treatment and 6 months after completion of treatment between patients who received nintedanib versus placebo.

3.3 Exploratory Objective:

- To investigate blood-based biomarkers in evaluating risk of developing radiation pneumonitis as well as the efficacy of nintedanib.

4 METHODOLOGY

[figure not shown]
5 STUDY DESIGN

A maximum of 18 participants will be enrolled to the Phase I non-randomized dose escalation portion of this study. See Figure 1 for the Phase 1 dose-escalation study schema.

A maximum of 99 participants will be enrolled to the randomized Phase II, double-blind, placebo-controlled portion of the study of nintedanib as prophylaxis against radiation pneumonitis in patients with advanced NSCLC. The study schema is depicted below.

[figure not shown]
All participants will sign an informed consent prior to study related tests. All participants will meet the inclusion and exclusion criteria summarized in **Section 6.1** and **Section 6.2**.

Figure 1 Phase 1 Dose-escalation Study Schema

For patients who will be receiving durvalumab consolidation treatment as standard of care prior to establishment of the recommended phase II dose of this combination, they will NOT undergo randomization (i.e. not blinded to treatment) and will receive active drug (nintedanib) on the first day of the first dose of durvalumab 10mg/kg every 2 weeks for up to 12 months.

Figure 2. Phase II Study Schema

§Patients will be stratified according to chemotherapy regimen (i.e., platinum with etoposide, platinum with taxane, platinum with pemetrexed) utilized concurrently with radiation as well as exposure to immune checkpoint inhibitor therapy.

§§An interim analysis for futility will be conducted when the first $n_1=33$ patients have completed 6-months of follow-up post-chemoradiation; that is, when the first $n_1=33$ patients are evaluable for the primary end-point (the rate of CTCAE Grade 2 or higher radiation pneumonitis at 6

months after completion of chemoradiation). If the estimated common odds ratio (COR) is greater than or equal to 0.8, then the study will stop early for futility. Otherwise, the study will continue and enroll an additional $n_2=66$ patients. Additionally, at this time the safety profile of the treatment arms may be evaluated and considered in the decision for study continuation.

5.1 Target Accrual and Study Duration

A maximum of 18 participants will be enrolled to the non-randomized dose escalation portion of this study. The number of participants required is a function of the unknown dose-toxicity relationship.

A maximum of 99 participants will be enrolled to the randomized Phase 2 portion of this study (excluding patients replaced due to ineligibility or inability to start therapy).

Participants will be enrolled from up to 4 sites including Roswell Park. Accrual is expected to take up to 4 years.

6 PARTICIPANT SELECTION

6.1 Inclusion Criteria

- 1 Age 18 years or greater.
- 2 Histologically or cytologically-proven non squamous cell NSCLC. Mixed histology with SCLC component not allowed.
- 3 Patients with Stage II - IV non squamous cell NSCLC who received at least 54 Gy of total planned thoracic radiation dose will be eligible. Patients must have received at least one cycle of chemotherapy concurrently during the course of thoracic radiation. Regimens allowed are platinum combinations with either etoposide or a taxane regardless of histology subtype; platinum with pemetrexed for patients with nonsquamous NSCLC only. Patients with oligometastatic Stage IV cancer are eligible if they have received only one line of systemic therapy for their Stage IV cancer prior to the concurrent chemoradiation phase.
- 4 Patient must have had a CR/PR/SD, 4-6 weeks after completing last fraction of radiation therapy.
- 5 ECOG Performance Score 0 - 2 (**Appendix C**).
- 6 ANC $\geq 1,500/\mu\text{L}$.
- 7 Platelet count $\geq 100,000/\mu\text{L}$.
- 8 Hemoglobin ≥ 9 g/dL.
- 9 Total bilirubin \leq normal or for those with Gilbert's syndrome ≤ 1.5 times upper limit of normal (ULN) OR direct bilirubin normal (per institute standards).
- 10 AST $\leq 1.5 \times$ ULN. ALT and AST $\leq 2.5 \times$ ULN is acceptable if there is liver metastasis.
- 11 Fertile patients must use adequate contraception.

6.2 Exclusion Criteria

- 1 WBRT < 14 days from the anticipated start of nintedanib/placebo administration.
- 2 Squamous cell NSCLC

- 3 Unable to start nintedanib/placebo treatment between 4 – 8 weeks after completing the last dose of thoracic radiation.
- 4 Active untreated brain or leptomeningeal metastases. In patients with treated CNS metastases, eligible if symptoms controlled for at least 4 weeks. Dexamethasone allowed if total daily dose does not exceed 2 mg.
- 5 Major injuries or surgery (e.g., craniotomy) <28 days from the start of nintedanib/placebo administration. Wound should be healed prior to starting therapy.
- 6 Second malignancies are allowed as long as the disease does not require active treatment with concomitant systemic cytotoxic chemotherapy, investigational or biologic therapy (e.g., anti-CTLA4 or HER2 monoclonal antibodies). Hormone-related therapies (e.g., LHRH agonists, tamoxifen, etc.) are allowed.
- 7 Concurrent uncontrolled illness including, but not limited to, ongoing or active infection, symptomatic congestive heart failure, unstable angina pectoris, cardiac arrhythmia, or psychiatric illness/social situation that would increase the risk associated with study participation and/or limit compliance with study requirements.
- 8 Inability to swallow study medication.
- 9 Presence of active malabsorption disorder (e.g., flare episodes documented within the preceding 3 months, presence of symptoms requiring daily medications for control) or history of extensive small bowel resection.
- 10 Known bleeding or thrombotic diathesis.
- 11 History of arterial or venous thromboembolic event within 12 months prior to study participation.
- 12 Active hemoptysis or history of clinically relevant hemoptysis as determined by the treating physician. Patients who had history of transient minor hemoptysis after bronchoscopic biopsy are eligible unless deemed otherwise by the treating physician.
- 13 CTCAE Grade 2 or higher proteinuria.
- 14 Investigational agent administered < 28 days prior to treatment with nintedanib. Last dose of systemic chemotherapy administered < 14 days prior to treatment with nintedanib.
- 15 Known chronic active hepatitis B or hepatitis C. HIV-positive patients receiving or are candidates for antiretroviral therapy are also excluded.
- 16 Pregnancy or breast feeding. Female patients with child-bearing potential must have a negative pregnancy test (β -HCG test in urine or serum) prior to commencing study treatment.
- 17 Creatinine > 1.5 x ULN or CrCL < 45 mL/min. Refer to Appendix D.
- 18 Centrally located tumors with radiographic evidence (CT or MRI) of local invasion of major blood vessels.
- 19 Therapeutic anticoagulation (except low-dose heparin and/or heparin flush as needed for maintenance of an in-dwelling intravenous device) or anti-platelet therapy (except for low-dose therapy with acetylsalicylic acid < 325 mg/day).
- 20 Active or previous autoimmune disease requiring treatment within the past 2 years will exclude patients from receiving immune checkpoint inhibitor in this study. Exception allowed: Endocrine conditions treated with necessary hormone replacement or other supportive medication; vitiligo, alopecia.

6.3 Inclusion of Women and Minorities

Both men and women and members of all races and ethnic groups are eligible for this study.

7 TREATMENT PLAN

7.1 Dosing and Administration

Treatment will be administered on an outpatient basis. Each cycle will be 28 days. Patients will be dispensed sufficient supply for at least 28 days or until their next scheduled visit. Reported adverse events (AEs) and potential risks are described in **Section 1.6**. Appropriate dose modifications are described in **Section Error! Reference source not found.**

With the November 2018 amendment allowing immune checkpoint inhibitor such as durvalumab consolidation therapy, a conventional dose-escalation design will be explored for patients who will be receiving durvalumab. Patients enrolled in the dose-escalation portion must commence nintedanib dosing at the same time as durvalumab is started. Dosing with nintedanib will start at 100 mg BID (see Table 1).

For patients who will be receiving durvalumab as standard of care prior to establishment of the recommended phase II dose of this combination, they will NOT undergo randomization (i.e. not blinded to treatment) and will receive active drug (nintedanib) on the first day of the first dose of durvalumab 10mg/kg every 2 weeks for up to 12 months.

All administered doses of the study drugs will be recorded in a pill diary to be provided to the patient (**Appendix E**).

7.1.1 Nintedanib

During Phase I dose escalation the participant will not be blinded to treatment and will receive active nintedanib according to the dose level assigned.

During Phase II, the participant will be randomized to receive either nintedanib or matched placebo.

The capsules of the defined dose (or placebo during Phase II) should be swallowed unchewed with a glass of water of about 250 mL or 8 oz. The dose interval should be of around 12 hours at the same times every day, usually in the morning and the evening after food intake.

In case of a missed dose, patients should proceed with the intake of medication according to the predefined schedule and take the next scheduled dose when it is due. Do not replace missed dose. All administered doses will be recorded in a pill diary to be provided to the patient (**Appendix E**).

7.1.2 Durvalumab

During dose escalation, the first two doses of durvalumab (10 mg/kg) will be given intravenously (IV) every 2 weeks over 60 minutes. These doses will be administered together with Cycle 1 Day 1 and day 15 (-1/+7 days) doses of nintedanib. Subsequent doses will be administered according to institutional practice.

During phase II, use of an immune checkpoint inhibitor (durvalumab), in the post-chemoradiation consolidation period is at the discretion of the treating physician.

7.2 Phase I

Dose escalation will proceed in a 3+3 fashion. Standard 3+3 rules will be followed until the maximum tolerated dose (MTD) is found. A total of 3 dose levels will be explored, with the MTD defined as the dose level wherein no more than 1 out of 6 patients evaluable for dose limiting toxicities (DLTs) experienced treatment-related DLT (Table 1).

Initially, 3 patients are enrolled at dose level 1. If no dose DLTs are observed, then 3 new patients are escalated to dose level 2. If ≥ 2 DLTs are observed at dose level 1, then dose-escalation stage is completed and study will be terminated.

If 1 DLT is observed, an additional 3 patients are enrolled at dose level 1. In those 6 patients at dose level 1, if ≤ 1 DLTs are observed attributable to the combination or nintedanib alone, we will proceed to dose level 2; otherwise, the study will be terminated if ≥ 2 DLTs are observed at dose level 1. If ≥ 2 DLTs are observed at dose level 2, the prior dose level (level 1) will be expanded to total of 6 patients if it has not been done yet. Otherwise, if 0-1 DLTs are observed at dose level 2, we proceed to dose level 3. The same basic principles are followed until the dose determined as the MTD is identified to use in Phase II.

Dose-limiting toxicities (DLTs) are as defined in Section 7.2.3. Once the MTD is determined, subsequent patients receiving durvalumab will be randomized to either nintedanib at MTD or placebo (Phase II). Nintedanib may also be started for subsequent patients at any time point (i.e. one or more durvalumab doses maybe given in the consolidation phase before protocol treatment is started) provided other eligibility criteria are met.

Table 1 Dose escalation scheme for the combination of nintedanib with durvalumab (Phase I)

Dose Level	Nintedanib Dose	Durvalumab dose
1	100 mg BID	10mg/kg every 2 weeks
2	150 mg BID	10mg/kg every 2 weeks
3	200 mg BID	10mg/kg every 2 weeks

7.2.1 Definition of DLTs for the Combination of Nintedanib with Durvalumab

A DLT is defined by the occurrence of toxicities outlined below attributable to either Nintedanib alone or the combination of Nintedanib plus durvalumab. Toxicity will be assessed using the NCI Common Toxicity Criteria for Adverse Events (CTCAE) version 4.03. DLTs must be scored as possibly, probably, or definitely related to either Nintedanib alone or the combination of Nintedanib plus durvalumab within the first 28 days of combination treatment. Patients who developed significant DLTs deemed possibly, probably or definitely related to Nintedanib (alone or in combination) will be taken off study.

- Nausea of CTCAE Grade ≥ 3 , despite maximal supportive care

- Vomiting of CTCAE Grade ≥ 3 , despite maximal supportive care
- Diarrhea of CTCAE Grade ≥ 3 of any duration despite maximal supportive care
- AST and/or ALT $> 5x$ ULN regardless of total bilirubin level
- AST and/or ALT $> 2.5x$ ULN together with total bilirubin $> 1.5x$ ULN (or $1.5x$ baseline in patients with Gilbert's syndrome)
- Other non-hematological adverse event of CTCAE Grade ≥ 3 considered drug-related and clinically significant (except transient electrolyte abnormality, alopecia, untreated vomiting or diarrhea, and isolated elevation of gamma glutamyl transpeptidase which will not be considered as DLT)
- CTCAE grade 4 Neutropenia and fever $\geq 38.5^{\circ}\text{C}$
- Neutropenia CTCAE Grade 4 for more than 7 days, without fever $> 38.5\text{ C}$
- Platelets CTC grade 4 or CTC grade 3 associated with bleeding or requiring transfusion
- Grade > 2 proteinuria
- Nintedanib $< 50\%$ of prescribed dose for the first cycle or inability to resume nintedanib dosing within 14 days of stopping due to treatment-related toxicity
- Durvalumab < 2 doses received

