9.2 Baseline Evaluations

The following will be performed within 4 weeks prior to first dose of study drug:

- Medical history
- Smoking History (Type of Tobacco/Nicotine Product [cigarettes, cigars, pipes, chew tobacco, nicotine gum, nicotine patch, other], current use, how long ago product use stopped.)
- Physical examination, including vital signs (i.e., temperature, heart rate, respiratory rate, blood pressure, body weight, and height)
- Hematology [(i.e., complete blood count (CBC) with automated differentials)](or, the physicians' discretion): WBC, RBC, HGB, HCT, platelet, MCV, MCH, MCHC, % neutrophils, absolute neutrophils, % monocytes, absolute monocytes, % eosinophils, absolute eosinophils, % basophils, absolute basophils, % lymphocyte total, absolute lymphocyte total, platelet confirmation (as clinically indicated), and differential confirmation (as clinically indicated). Note: Participants experiencing Grade 4 neutropenia should be monitored according to institutional guidelines. As needed at each study visit as determined by the Investigator or study physician.
- Chemistry (i.e., complete metabolic panel (CMP): chloride, CO₂, potassium, sodium, BUN, glucose, calcium, creatinine, total protein, albumin, total bilirubin, alkaline phosphatase, AST, ALT, A/G ratio, BUN/creatinine ratio, osmol (Calc), anion gap).
- Pulmonary Function Test
- ECOG Performance Status (Appendix C)
- Urinalysis to assess proteinuria
- Tumor/Disease Assessment

- Concomitant Medications: List any ongoing medications with an onset within 1 week of first dose of study drug.
- Adverse Events

9.3 Evaluations Performed at Cycle 1 Day 1

The following will be performed on Cycle 1 Day 1 or within 7 days prior to drug administration:

- Medical history
- Physical examination, including vital signs (i.e., temperature, heart rate, respiratory rate, blood pressure, and body weight)

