9.10 Schedule of Procedures and Observations

The schedule of procedures and observations for this study is summarized in Table 5 below.

Table 5 Schedule of Procedures and Observations

Evaluation	Baseline ¹	Active Treatment Stage			Surveillance Stage			
		Cycle 1 Day 1 (or within 7 days prior to drug administration)	Cycle 2 through Cycle 6 Day 1 (± 7 days)	Anytime when radiation pneumonitis is suspected to have occurred (within the first 6 months after completing radiation therapy)	End of Active Treatment (within 30 days of last nintedanib dose)	Between 76 to 97 days after last nintedanib dose	Between 166 to 187 days after last nintedanib dose	Long Term Follow-Up ²
Medical History	X	X	X	X	X	X	X	X
Smoking History	X							
Pre-Existing Conditions	X							
Physical Examination, including vital signs (i.e., temperature, heart rate, respiratory rate, blood pressure, body weight, height) ³	X	X	X	X	X	X	X	X
Hematology ⁴	X	X	X	X	X		X	X
Chemistry ⁵	X	X	X	X	X		X	X
25-OH Vitamin D level (Section 9.12)		X						
Mitochondrial DNA and Cytokine Assay (Section 9.11) ⁹		X	X ⁷	X		X		
miRNA Biochip Assay (Section 9.12)		X						
Pulmonary Function Test	X				X		X	
QOL Questionnaire (Appendix F)		X	X ⁷	X	X	X	X	X
Pregnancy Test (Urine or Serum) ¹¹		X						

Evaluation	Baseline ¹	Active Treatment Stage			Surveillance Stage			
		Cycle 1 Day 1 (or within 7 days prior to drug administration)	Cycle 2 through Cycle 6 Day 1 (± 7 days)	Anytime when radiation pneumonitis is suspected to have occurred (within the first 6 months after completing radiation therapy)	End of Active Treatment (within 30 days of last nintedanib dose)	Between 76 to 97 days after last nintedanib dose	Between 166 to 187 days after last nintedanib dose	Long Term Follow-Up ²
Urinalysis ¹⁰	X							
ECOG Performance Status (Appendix C)	X	X	X	X	X	X	X	X
Tumor/Disease Assessment ⁶	X		X ⁷	X		X	X	X
Study Drug/Placebo		X	X					
Durvalumab		X ¹²						
Concomitant Medications	X ⁸	X	X	X	X	X	X	X
Adverse Events	X	X	X	X	X			

Evaluation	Baseline ¹	Active Treatment Stage			Surveillance Stage			
		Cycle 1 Day 1 (or within 7 days prior to drug administration)	Cycle 2 through Cycle 6 Day 1 (± 7 days)	Anytime when radiation pneumonitis is suspected to have occurred (within the first 6 months after completing radiation therapy)	End of Active Treatment (within 30 days of last nintedanib dose)	Between 76 to 97 days after last nintedanib dose	Between 166 to 187 days after last nintedanib dose	Long Term Follow-Up ²

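### Phase I DLTs count only on days 1–28, but no post-dose blood panel is required by day 28, so a liver-enzyme DLT can be missed or left in doubt

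*Combined protocol and SAP*

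**What the plan says.** **DLT window.** Section 7.2.1 lists 12 DLT criteria and counts an event if it is at least possibly related to nintedanib, alone or in combination, and falls "within the first 28 days of combination treatment". Two criteria are liver-enzyme thresholds. Others include "Neutropenia CTCAE Grade 4 for more than 7 days, without fever" above 38.5 °C, Grade 4 platelets, proteinuria above Grade 2, and "inability to resume nintedanib dosing within 14 days of stopping due to treatment-related toxicity".

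**Decision rule.** Section 7.2 uses 3+3 rules over 100, 150 and 200 mg BID: "If no dose DLTs are observed, then 3 new patients are escalated to dose level 2". The MTD is the level at which "no more than 1 out of 6 patients evaluable for dose limiting toxicities (DLTs) experienced treatment-related DLT". Durvalumab patients in Phase II are then randomised to that dose or placebo.

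**Laboratory schedule.** Section 7.1: "Each cycle will be 28 days". Under Section 9.3, the first on-study panel is "performed on Cycle 1 Day 1 or within 7 days prior to drug administration". The next column in Table 5 that applies to every patient is "Cycle 2 through Cycle 6 Day 1 (± 7 days". The second durvalumab dose is due on day 15 (−1/+7 days) under Section 7.1.2, with no laboratory test attached. Table 5 footnote 10 leaves urinalysis after baseline to clinical judgement.

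**The concern.** The counting window and the blood-draw schedule do not meet. A patient treated exactly to protocol can finish the 28 days with no post-dose laboratory result. Some DLTs cause no symptoms and can be found only by a test.

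Liver enzymes matter most. Section 1.4.1 says nintedanib's dose-limiting toxicities were mainly reversible enzyme elevations. Section 2 reports three liver-enzyme DLTs at 200 mg BID when nintedanib was combined with pembrolizumab, and that study settled on 150 mg BID. This trial escalates to 200 mg BID.

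An event that is missed, or measured but not counted, can only lower the DLT count. The bias therefore runs towards escalation and a higher MTD, in a part of the trial whose primary objective is safety.

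**Working it through.** **Plan's own figure.** 3 dose levels × 6 patients = 18, the stated Phase I maximum. It reproduces.

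**Visit days**

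1. DLT window (7.2.1): days 1–28.
2. Cycle 2 Day 1 (28-day cycles, 7.1): 1 + 28 = day 29.
3. Allowed range (Table 5, ±7): 29 − 7 = 22 to 29 + 7 = 36, which is 15 days.
4. Inside the window: days 22–28 = 7. After it: days 29–36 = 8, including the nominal day.
5. If a pre-dose day-29 draw counts as end of first cycle, days 30–36 = 7 of 15 remain outside.
6. Second durvalumab dose (7.1.2): 15 − 1 = 14 to 15 + 7 = 22, so always inside the window, but without a panel.
7. Required by day 28: 0 post-dose chemistry or haematology panels. Required after baseline: 0 urinalyses.

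**Which DLTs can be silent.** Five of the 12: the two liver criteria, prolonged Grade 4 neutropenia without fever, Grade 4 platelets without bleeding, and proteinuria. They do not carry equal risk, and only the liver criteria have strong support in the background sections. Grade 4 neutropenia with fever and Grade 3 platelets with bleeding would show clinically and are not at issue.

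**Duration-based criteria**

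- Afebrile Grade 4 neutropenia first counted on day 22 passes 7 days on day 30, after the window. First counted on day 15, it passes on day 23. Section 7.2.1 does not say whether onset or the whole duration must fall inside the window.
- If nintedanib is stopped on day 15, the 14-day resumption limit is reached on 15 + 14 = day 29. The list therefore already contains an item that may not resolve until the cycle has ended.

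**What one event changes (7.2)**

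| Counted DLTs | Action |
|---|---|
| 0 of 3 | escalate |
| 1 of 3 | enrol 3 more at the same level |
| 1 of 6 | level acceptable |
| 2 of 6 | level not acceptable (at level 1, the study terminates) |

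One uncounted event is enough to move a cohort between adjacent rows in either pair. Putting a probability on that would need the true DLT rate and the share of DLTs detected. The documents give neither.

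**The case against.** **Day 29 may well count.** A draw before the Cycle 2 dose reflects exactly 28 days of treatment and only first-cycle exposure. The DLT item on receiving under half the first-cycle dose also needs the whole cycle. This reading is sensible and reduces most of the liver gap to wording. It is not written down, and it leaves draws on days 30–36, the missing mid-cycle panel and proteinuria unresolved.

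**A liver rise would probably still be visible.** Dosing is continuous and the elevations reversed after stopping, so a rise in a patient still on drug would probably persist to the day 22–36 draw. Section 1.4.1 also describes a very low incidence below 200 mg. Both points stand; the concern is mainly at 200 mg BID.

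**Other text calls for monitoring.** Section 1.6 demands close follow-up of liver enzymes, Section 7.4.4 recommends it, and the haematology note allows tests as needed. That note also sends Grade 4 neutropenia to institutional guidelines, so once a low count is found its duration would be followed. Appendix B requires repeat liver tests within 48 hours and at least weekly follow-up, but only after an abnormal result. The suspected-pneumonitis visit includes a panel only when that suspicion arises. Section 9 defers procedures not otherwise defined to institutional procedures that are not in the documents. None of the text available fixes a first in-window draw.

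**Stronger readings that the documents do not support**

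- *Late events would go unseen.* Section 11.1.3 reports Phase 1 events of all grades, Section 11.3 expedites liver events of special interest, Section 12 provides programme review, and Section 17.2 allows termination for safety. These could act on a late event, although none is a stated escalation rule.
- *The next cohort opens before the last is assessed.* Appendix A requires an open slot before consent and does not mention Cycle 1 laboratory results. That is silence, not permission.
- *8 of 15 is the chance of a late draw.* It counts allowed days and says nothing about how visits will fall.

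**Conclusion.** The gap is real and should be fixed. By the text, no post-dose blood panel is required by day 28; 8 of the 15 allowed days for the next one (7 if day 29 counts) fall after the window; and no urinalysis is required after baseline. The main consequence is that a liver-enzyme DLT first measured on days 29–36 is not clearly counted, and a silent one may be missed. Neutropenia and proteinuria are lesser concerns.

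A reader might infer that the MTD will be set too high. The documents fix only the direction of the possible bias and the fact that one event can change a decision; they give no basis for a size. The conclusion takes the 28 days and Table 5 as written and assumes that unscheduled draws cannot be relied on for every patient. If sites routinely draw blood before the day-15 infusion, the practical gap is smaller, but the protocol does not require them to. At most 18 patients are affected directly; later durvalumab patients are affected through the dose they receive.

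**What to change.** For the Phase I cohort only, amend Sections 7.2, 7.2.1, 9.3–9.4 and Table 5:

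1. Define the DLT period as days 1–28, extended through the pre-dose Cycle 2 Day 1 assessment if that is later, and never ending before day 28.
2. Remove both the −7 and the +7 allowance on the Cycle 2 Day 1 laboratory tests, so that they are drawn on day 28 or 29 before the Cycle 2 dose. Removing only the +7 would leave a day-22 draw compliant, with days 23–28 uncovered. Count duration-based DLTs by onset date.
3. Draw the existing chemistry and haematology panels at the day-15 durvalumab visit. At its latest (day 22) this is still 28 − 22 = 6 days before the end-of-cycle draw, so the two cannot collapse into one.
4. Make the next dose-level decision only when the Cycle 2 Day 1 results of every patient in the cohort are available.

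A Cycle 2 Day 1 urinalysis is an optional, low-cost addition. Section 7.2 also points to 7.2.3 for the DLT definition, which is in 7.2.1; correct this at the same time.

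Cost: protocol wording, one routine blood draw at a visit that already occurs, tighter visit timing and a short wait between cohorts, for at most 18 patients. Counting the Cycle 2 Day 1 results needs no new test.
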